9.5.4. Urine routine examination

Table 76. Shift-table of urine routine examination results before and after treatment-Leukocyte

Table 77. Shift-table of urine routine examination results before and after treatment-Erythrocyte

Table 78. Shift-table of urine routine examination results before and after treatment-pH

Table 79. Shift-table of urine routine examination results before and after treatment-Urine protein

Table 80. Shift-table of urine routine examination results before and after treatment-Color

Table 81. Shift-table of urine routine examination results before and after treatment-Definition

9.5.5. Serum biochemistry

Table 82. Shift-table of serum biochemistry results before and after treatment-Glutamyl transpeptidase (GT)

Table 83. Shift-table of serum biochemistry results before and after treatment-Alanine aminotransferase (ALT)

Table 84. Shift-table of serum biochemistry results before and after treatment-Aspartate aminotransferase (AST)

Table 85. Shift-table of serum biochemistry results before and after treatment-Lactate dehydrogenase

Table 86. Shift-table of serum biochemistry results before and after treatment-Total bilirubin

Table 87. Shift-table of serum biochemistry results before and after treatment-Direct bilirubin

Table 88. Shift-table of serum biochemistry results before and after treatment-Alkaline phosphatase

Table 89. Shift-table of serum biochemistry results before and after treatment-Scr

Table 90. Shift-table of serum biochemistry results before and after treatment-Uric acid

Table 91. Shift-table of serum biochemistry results before and after treatment-Blood urea nitrogen

Table 92. Shift-table of serum biochemistry results before and after treatment-Cystatin C

Table 93. Shift-table of serum biochemistry results before and after treatment-Fasting blood glucose

Table 94. Shift-table of serum biochemistry results before and after treatment-Total cholesterol

Table 95. Shift-table of serum biochemistry results before and after treatment-Triglyceride

Table 96. Shift-table of serum biochemistry results before and after treatment-Total protein

Table 97. Shift-table of serum biochemistry results before and after treatment-Albumin

Table 98. Shift-table of serum biochemistry results before and after treatment-Globulin

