Respiratory, chest and mediastinum abnormalities

Common: Dyspnea, abnormal lung parenchyma, pleural effusion, pharyngitis, cough, nasal congestion and inflammation; Unusual: Respiratory failure, respiratory diseases, and asthma; Rare: Acute respiratory distress syndrome; Unknown: Interstitial lung disease, and pulmonary embolism.

Gastrointestinal abnormalities

Very common: Diarrhea, and nausea; Common: Gastrointestinal inflammation, gastrointestinal ulcer and perforation, gastrointestinal bleeding, stomatitis and ulcer, ascites, vomiting, abdominal pain, dyspepsia, constipation, abdominal distention, loose stools and other gastrointestinal symptoms and signs; Unusual: Paralytic intestinal obstruction, peritonitis, acute and chronic pancreatitis, elevated blood amylase, gastroesophageal reflux and abnormal gastric emptying; Rare: Intestinal obstruction, and pancreatic pseudocyst.

Renal and urinary abnormalities

Very common: Kidney injury; Common: Renal failure, oliguria, tubular necrosis, toxic nephropathy, and bladder and urethral symptoms; Unusual: Anuria, and hemolytic uremic syndrome; Very rare: Kidney disease, and hemorrhagic cystitis; Unknown: Membranous glomerulonephritis, hydronephrosis, nephromegaly, and nephrotic syndrome.

Skin and subcutaneous tissue abnormalities

Very common: Pruritus, rash, hair loss, acne, and hyperhidrosis; Unusual: Dermatitis, and photosensitivity; Rare: Toxic epidermal necrolysis (Lyell's syndrome); Very rare: Stevens-Johnson syndrome; Unknown: Melanoderma.

Skeletal muscle and connective tissue abnormalities

Common: Joint pain, muscle spasm, limb pain, and back pain; Unusual: Joint disorder; Unknown: Bone defect, kyphosis, patellar pain syndrome, and rhabdomyolysis.

Endocrine abnormalities

Rare: Hirsutism; Unknown: Diabetes ketoacidosis.

Metabolic and nutritional abnormalities, and other electrolyte abnormalities

Very common: Hyperglycemia, diabetes, and hyperkalemia; Common: Hypomagnesemia, hypophosphatemia, hypokalemia, hypocalcemia, hyponatremia, fluid retention, hyperuricemia, decreased appetite, anorexia, metabolic acidosis, hyperlipidemia, hypercholesterolemia, and hypertriglyceridemia. Other electrolyte abnormalities: Unusual: Dehydration, hypoproteinemia, hyperphosphatemia and hypoglycemia.

Infection and invasion

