9.5.3. Blood routine examination

Table 69. Summary of blood routine examination-Leukocyte count (WBC)

Items	Indicator	Experimental group	Control group	Total
Visit 1/Day 0	Within the normal range n (%) Below the normal range n (%) Higher than the normal range n (%) Total (Missing) Statistics P-value			

Visit 9/Day 364±7	Within the normal range n (%)
	Below the normal range n (%)
	Higher than the normal range n (%)
	Total (Missing)
	Statistics
	P-value

Table 70. Summary of blood routine examination-Lymphocyte percentage (LY)

Items	Indicator	Experimental group	Control group	Total
Visit 1/Day 0	Within the normal range n (%)			
	Below the normal range n (%)			
	Higher than the normal range n (%)			
	Total (Missing)			
	Statistics			
	P-value			
Visit 9/Day 364±7	Within the normal range n (%)			
	Below the normal range n (%)			
	Higher than the normal range n (%)			
	Total (Missing)			
	Statistics			
	P-value			

Table 71. Shift-table of blood routine examination results before and after treatment-Leukocyte count (WBC)

Group	Before treatment	Day 364±7 after treatment					Not tested	Missing	Total
		Normal	Abnormal but not clinically significant	Abnormal and clinically significant					
Experimental group	Normal								
	Abnormal but not clinically significant								
	Abnormal and clinically significant								
	Not tested								

	Missing
	Total
Control group	Normal
	Abnormal but not clinically significant
	Abnormal and clinically significant
	Not tested
	Missing
	Total

Table 72. Shift-table of blood routine examination results before and after treatment-Erythrocyte count (RBC)

Ibid. Same below.

Table 73. Shift-table of blood routine examination results before and after treatment-Haemoglobin (Hb)

Table 74. Shift-table of blood routine examination results before and after treatment-Platelet count (PLT)

Table 75. Shift-table of blood routine examination results before and after treatment-Lymphocyte percentage (LY)

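### The blood-count and serum shift tables do not separate low from high results, and only 2 of the 22 tests have low/high counts on the safety set

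*SAP*

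**What the plan says.** SAP section 9.5 is the safety analysis on the safety set (SS). Within it, section 9.5.3 gives one shift-table shell, Table 71 for leukocytes. Its classes, before treatment and at Day 364, are normal, "Abnormal but not clinically significant", "Abnormal and clinically significant", not tested and missing. The note "Ibid. Same below" under Table 72 carries that layout forward. The serum tables in section 9.5.5 (Tables 82-98) are titles only, for example "Table 93. Shift-table of serum biochemistry results before and after treatment-Fasting blood glucose", so their layout has to be read from Table 71.

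In the same section, Tables 69 and 70 do show direction. Besides a within-range row they have the rows "Below the normal range n" and "Higher than the normal range n" (each with a percentage), plus a statistic and a P value, at Visit 1 and Visit 9. They cover leukocyte count and lymphocyte percentage only.

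Protocol section 8.1.1 lists the tacrolimus reactions of concern. For glucose it names both directions: "Very common: Hyperglycemia, diabetes, and hyperkalemia" and, further on, "Unusual: Dehydration, hypoproteinemia, hyperphosphatemia and hypoglycemia". It also names both leucopenia and leucocytosis.

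**The concern.** A shift table should show how many children in each arm moved out of range on a given test. For a two-sided test such as glucose, low and high are different clinical events. If the table adds them together, the count cannot say which event occurred, and a difference or similarity between arms in that count has no clear meaning. The trial aims to identify the safer of two drugs, so safety-set tables that count abnormal results without direction are less useful than they could be. The SAP already contains a layout that shows direction and applies it to two tests, without saying why the others are left out.

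**Working it through.** No sample size, power or event-rate figure is involved. The check compares table layouts and counts tests.

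**Step 1: what a shift cell holds.** For significance grade *g* (not clinically significant, or clinically significant), the Table 71 cell for a move from normal is

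n(normal → abnormal, *g*) = n(normal → low, *g*) + n(normal → high, *g*).

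Only the sum is reported. An arm with *a* high and *b* low results and an arm with *b* high and *a* low results would have the same entry in that cell.

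**Step 2: how many tests.** Blood-count shift tables 71-75 cover 5 tests (leukocytes, erythrocytes, haemoglobin, platelets, lymphocyte percentage). Serum shift tables 82-98 cover 98 − 82 + 1 = 17. The total is 5 + 17 = 22. Tables 69-70 give a low/within/high count for 2 of them, leaving 22 − 2 = 20 without one: erythrocytes, haemoglobin, platelets and all 17 serum tests.

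**Step 3: where else direction appears.**

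| Output | Tests covered | Population | Direction shown? | What it does not give |
|---|---|---|---|---|
| Shift tables 71-75, 82-98 | 22 | SS | No | Low and high separately |
| Tables 69-70 | 2 | SS | Yes, as counts with a P value | The other 20 tests |
| Change-from-baseline tables 24-27, 35-38, 41-54 | 4 + 4 + 14 = 22 | FAS/PPS | Yes, signed change | Number of children low or high; the safety set |
| Listings 121 and 123 | Blood routine and serum | SS | Yes, child by child | Counts by arm; children already abnormal at baseline |
| Adverse-event tables 65-66 | Clinically significant changes | SS | Normally, through the coded term | Changes graded not clinically significant |

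The change tables take their layout from Table 23, by the carry-forward note under Table 24. That layout has mean, median, quartiles, minimum, maximum, a 95% CI and a between-arm comparison of the change. Glucose is Table 50. The adverse-event route comes from SAP section 8.1.6, which counts clinically significant laboratory changes as adverse events and codes them in MedDRA.

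**Step 4: whether FAS/PPS can stand in for the safety set.** SAP section 7.1 removes eliminated cases from the FAS but keeps some of them in the SS. Under section 4.5.3, elimination covers adherence below 80% or above 120% and changing the dose at will. A child with unusual drug exposure can therefore be in the shift tables, where direction is not shown, and absent from the change tables, where it is. The documents do not allow an estimate of how many such children there will be.

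**Step 5: where the protocol expects both directions.** Among the 22 tests, section 8.1.1 names both a rise and a fall for glucose and for leukocytes. Leukocytes are already covered by Table 69. For other tests it names one direction, such as thrombocytopenia, anaemia, hypoproteinaemia, raised lipids and hyperuricaemia. That leaves glucose as the test most affected.

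**The case against.** The best defence is that a shift table by clinical significance is a legitimate layout and that the SAP does not rely on it alone. All 22 tests have signed change tables with a between-arm comparison. If the two drugs moved glucose in opposite directions, Table 50 is where that would be expected to appear. Listing 123 prints the values for children who went from normal to abnormal. A clinically significant high or low glucose would be an adverse event with its own coded term, with incidence and a P value by arm. For most tests the protocol expects one direction, so a reader can often guess what abnormal means.

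Most of this stands, and it rules out some stronger readings that a reader might infer:

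- That the shell has a single abnormal class. It has two, split by clinical significance.
- That opposite drug effects would be indistinguishable in the report. This can happen within a shift table, but the other outputs in Step 3 carry direction.
- That a planned significance test would mislead. The Table 71 shell has no statistic or P-value row.
- That the arms are expected to push glucose in opposite directions. Both glucose reactions are listed under tacrolimus, and the MMF list in Protocol section 8.1.2 names no glucose effect.

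The other outputs still leave something open. A mean or median change does not count children out of range and can hide opposite tails within one arm. The listings give no arm totals and omit a child who moves from low at baseline to high. The adverse-event route depends on a judgement of clinical significance made in an open-label trial, and it misses everything graded not significant.

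**Conclusion.** The point holds in a limited form. The shift tables for 22 blood and serum tests carry no direction, and 20 of those tests have no count of low and high results on the safety set. Fasting glucose is the clearest case. For the other 19 the practical loss is smaller, because where the protocol names a reaction it names one direction. The documents do not show that the arm comparison of laboratory harm would come out wrong, and the primary analysis is unaffected. This is a minor weakness in safety reporting and a cheap improvement.

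The conclusion rests on one inference: that the carry-forward note under Table 72 applies the Table 71 layout to Tables 82-98, which have no shell of their own.

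**What to change.** Do one of the following, on the safety set and by arm, with both directions reported:

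- Extend the below/within/above-range format of Tables 69-70 to the other 20 tests. For the first time point use the baseline value instead of Visit 1, because the protocol's flow chart marks fasting glucose at screening and not at Visit 1.
- Or split each of the two abnormal classes in the Table 71 shell into low and high. This takes the shell from 5 classes to 7, that is from 5 × 5 = 25 to 7 × 7 = 49 body cells per arm, and also shows moves from low to high.

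Neither option needs new measurements, since the change tables and listings already require the numeric results. Both assume that each site's reference limits are available for the 20 tests. Tables 69-70 imply this for two tests, and the documents do not say for the rest. The other cost is somewhat longer tables.

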9.5.6. DNA/antibody test

Table 99. Shift-table of DNA/antibody test results before and after treatment-Blood EBV-DNA

Table 100. Shift-table of DNA/antibody test results before and after treatment-IgM

Table 101. Shift-table of DNA/antibody test results before and after treatment-IgG

9.5.7. Urine test

Table 102. Shift-table of urine test results before and after treatment-24hr urine protein (>3 years old)

Table 103. Shift-table of urine test results before and after treatment-Urine protein/creatinine

9.5.8. Glomerular filtration rate

Table 104. Shift-table of eGFR results before and after treatment-eGFR

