8.3 Records of adverse events

The information of AEs to be collected in this research includes the following aspects:

- Endpoint event
- Adverse events related to the test drugs (according to the judgment of the investigators)
- Serious adverse event

Cycle of adverse event collection

The collection of AEs and adverse drug reactions (DAEs) of concern will be carried out throughout this research, from randomization to site close-out visit (SCV, included).

SAE records will be carried out throughout this research, from the time of signing the Informed Consent Form to SCV (included).

Follow-up of unresolved adverse events

If any AE, DAE and SAE of concern remain unresolved at the patient's last study visit, the investigators shall follow up these events in accordance with the medical instructions as required for medical needs in this research, but it is not necessary to record further in the electronic case report form (eCRF). If deemed necessary, the Sponsor reserves the right to obtain the additional information on unresolved AE/SAE of concern.

Variables

For each non-serious AE and DAE of concern, the following variables will be collected:

- AE (verbatim record);
- AE start and end dates;
- Maximum intensity;

- Whether the AE is serious;
- The investigators' assessment of the causal relationship with the test drug (yes or no);
- Measures and outcomes taken for the test drug

In addition, the following variables will be collected for SAE:

- Date when AE meets SAE criteria;
- Date when the investigators find SAE;
- Reasons for classifying AE as SAE;
- Date of admission;
- Date of discharge;
- Possible causes of death
- Date of death;
- Autopsy performed (if any);
- Autopsy results
- AE description
- Assessment of causality with this research procedure;
- Assessment of causality with the other drugs

It is important to distinguish serious AE from severe AE. Severity is the index of intensity evaluation, while seriousness is defined according to the criteria in Section 8.2. AE with severe intensity is not necessarily serious. For example, nausea for several hours may be considered as severe nausea, but not SAE. On the other hand, a stroke that results in only a limited degree of disability may be considered as a mild stroke, but should be considered as SAE.

The definition of intensity classification is as follows:

1. Mild (signs or symptoms are felt but easily tolerated)

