2. Moderate (the degree of discomfort is enough to interfere with normal activities)
3. Severe (resulting in disability and inability to perform normal activities)

Collection of causalities

The investigators will assess the causalities between the test drugs and each case of AE, and answer the following questions with "Absolutely related, Probably related, Possibly related, Possibly unrelated, and Unrelated".

"Do you think there is a reasonable possibility that the event is caused by the test drug?"

For SAE, the causalities between the event and other drugs and research procedures also need to be evaluated. Note: for SAE related to any research procedure, causality should be "possibly related".

Adverse events based on signs and symptoms

All concerned AEs (see sections 8.1.1 and 8.1.2), including those spontaneously reported by the patients, those reported in response to the open-ended question by the investigators, "Have you

had any health problems since the last visit/inquiry?", or those found through observation will be all collected and recorded in eCRF. In the collection of AE information, the list of signs and symptoms shall be preferred as the record of diagnosis (if possible). However, if the diagnosis is known and there are other signs or symptoms not usually present in the diagnosis, the diagnosis and each other sign or symptom shall be recorded separately.

Adverse events based on examination and inspection

During this research, the laboratory safety assessment will not be carried out routinely (except at baseline), but can be carried out at the discretion of the investigators. When an AE, DAE, SAE or potential endpoint of concern is involved, different assessments may be required, including local laboratory assessment, and appropriate collection is needed before entry into eCRF.

The examination results of vital signs mandated by the Protocol shall be summarized in the clinical study report (CSR). Therefore, when the laboratory test values and protocol-mandated vital signs evaluation by the investigators show that the results are worse than the baseline level and meet the AE criteria or when they act as are the reasons for discontinuing the test drug treatment, such situations will be reported as AE.

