4.2.2 Determination of the number of cases

It is estimated that 1-year relapse-free survival is 0.56 in MMF Group, and 0.70 in FK506 Group. The enrollment time of this research is expected to be 2 years, and the total time of this research is 3 years, with a test level $\alpha = 0.05$, and a power of test $1 - \beta = 80\%$. It is estimated to have 114 patients in MMF group and 115 patients in FK506 group, with a total of 229 patients. With the consideration of 15% loss of follow-up, a total of 270 patients are needed, including 135 patients in each group.

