8.1.5. Other analysis

- (1) Case distribution: Different data sets in each group, case distribution in each Site, comparison of total drop-off rate, detailed list of termination reasons, and descriptive analysis.
- (2) Compliance analysis: Compare whether the two groups of patients take the test drugs on time and in quantity, whether they take the drugs and foods prohibited in the Protocol, and conduct the same descriptive analysis as well as χ^2 test or Fisher test for analysis.
- (3) The incidence of drug withdrawal or drug change due to adverse reactions in the clinical trial shall be analyzed with χ^2 test or Fisher test. The efficacy in the long-term follow-up after the trial is evaluated by descriptive analysis and χ^2 test or Fisher test.

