9.1. Research overview

Table 1. Distribution of subjects at each site (All enrolled subjects)

Research Site	Group	No. of subjects enrolled	No. of subjects drop-out	Drop-out rate	No. of subjects eliminated	Elimination rate	No. of subjects completed
Site 1	Experimental group						
	Control group						
	Total						
Site 2	Experimental group						
	Control group						
	Total						
...							
Total	Experimental group						
	Control group						
	Total						

Note: 1. The Site name is not displayed in following table, only the site number. Same below. 2. No. of subjects completed = No. of subjects enrolled - No. of subjects drop-out. Elimination refers to subjects who complete the trial, but were not included in the PPS. Subjects who withdrew due to the endpoint event were considered to have completed the trial. 3. Drop-out rate = No. of subjects drop-out / No. of subjects enrolled; Elimination rate = No. of subjects eliminated / No. of subjects enrolled.

Table 2. Distribution of subjects at each site

Site	PPS			FAS			SS		
	Experimental group	Control group	Total	Experimental group	Control group	Total	Experimental group	Control group	Total
Site 1									
Site 2									
Total									

Table 3. Trial completion and distribution of analysis data set (All enrolled subjects)

Items	Indicator	Experimental group	Control group	Total
No. of subjects enrolled	Yes			
	No			
Complete 1 week follow-up	Yes			
	No			
Complete 4 week follow-up	Yes			
	No			
Complete 8 week follow-up	Yes			
	No			
Complete 16 week follow-up	Yes			
	No			
Complete 24 week follow-up	Yes			
	No			
Complete 32 week follow-up	Yes			
	No			
Complete 40 week follow-up	Yes			
	No			
Complete 52 week follow-up	Yes			
	No			
Trial completion	Yes			

Items	Indicator	Experimental group	Control group	Total
	No			
Treatment discontinuation reason	Subject voluntarily withdrew prematurely			
	Decision by the investigator			
	Poor compliance that decided by the investigator			
	Meet the exclusion criteria, or did not meet the inclusion criteria			
	Refusal to continue trial participation			
	Lack of efficacy			
	Adverse events			
	Lost to follow-up			
	Death			
	Other			
FAS				
PPS				
SS				

Note: Follow-up time (years) = (last visit date - random date + 1) / 365.25. Complete 1 week follow-up: follow-up duration \geq 1 week, and so on.

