Table 125. List of eGFR results that were normal before treatment and abnormal after treatment (SS)

Site	Subject code	Random number	Group	Visit	Baseline result	Baseline clinical judgment	Visit result	Visit clinical judgment

Table 126. List of chest X-ray results that were normal before treatment and abnormal after treatment (SS)

Site	Subject code	Random number	Group	Visit	Baseline result	Baseline clinical judgment	Visit result	Visit clinical judgment	Description of abnormal

Table 127. List of ECG examination results that were normal before treatment and abnormal after treatment (SS)

Site	Subject code	Random number	Group	Visit	Baseline result	Baseline clinical judgment	Visit result	Visit clinical judgment	Description of abnormal

Table 128. List of AE (SS)

Site	Subject code	Random number	Group	AE ID	Description of AE	Severity	Start date	Treatment or not	AE ended or not	End date	Treatment	Relationships	Measures taken on
												with drug	study drug

Table 129. List of AE-continued (SS)

Site	Subject code	Random number	Group	AE ID	Description of AE	AE outcomes	Recovery/cure date	Details of sequelae	Death date	SAE or not	Cause withdraw or not

Table 130. List of SAE (SS)

Site	Subject code	Random number	Group	SAE ID	Type of SAE	Report date	Description	SAE situations	Death date	Severity	Onset Date	SAE	Relationships with
							of SAE					outcomes	drug

Table 131. List of SAE-continued (SS)

Site	Subject code	Random number	Group	SAE ID	Type of SAE	Report time	Description	Measures taken on	Reported SAE situation	Details of SAE occurrence
							of SAE	study drug		and treatment

Table 132. List of concomitant medication (SS)

Site	Subject code	Random number	Group	CM	China approved	Administration	Single dose	Unit	Frequency	Purpose of	Dosing start date	Still in use	Dosing end date
				ID	drug names	route				medication

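### Safety-set renal and liver laboratory tables compare baseline only with Day 364, so no table counts, by arm, the children whose worst value at any visit crossed the plan's own levels

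*SAP*

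**What the plan says.** SAP 9.5 (safety set) reports liver and renal chemistry in Tables 82-92 and 96-98 and eGFR in "Table 104. Shift-table of eGFR results before and after treatment-eGFR". All follow the Table 71 shell in SAP 9.5.3. That shell crosses the pre-treatment category with the category at "Day 364±7 after treatment", by arm. The categories are clinical judgements (normal, abnormal without or with clinical significance) plus not tested and missing.

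The flow chart (SAP 4.4) schedules renal function, liver function and eGFR at Visits 2 to 9.

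The plan sets these numeric levels:
- **Withdrawal, renal (SAP 4.5.4, item 4):** creatinine more than twice baseline on two consecutive measurements at least 4 weeks apart, with eGFR below 60.
- **Tacrolimus halving (SAP 5.2.3.1):** creatinine up by at least 30% with eGFR below 60, non-drug causes excluded.
- **Liver (SAP 4.5.4, item 6):** ALT or total bilirubin above twice the upper limit, the start of a sequence that can end in stopping drug and withdrawal.

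Three other routes carry laboratory information:
- **Adverse events.** SAP 8.1.6 counts clinically significant laboratory changes as adverse events. Protocol 8.3 says of laboratory values that act as "the reasons for discontinuing the test drug treatment, such situations will be reported as AE". SAP 8.1.5 (3) compares "The incidence of drug withdrawal or drug change due to adverse reactions".
- **By-visit tables.** Tables 23-27 and 41-49 sit in the efficacy section on the FAS and PPS.
- **Listings.** Tables 123 and 125 list individual children; the latter is headed "List of eGFR results that were normal before treatment and abnormal after treatment (SS").

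**The concern.** Safety is a stated objective. The protocol background presents MMF as free of nephrotoxicity, while Protocol 8.1.1 lists kidney injury as very common with tacrolimus. A reader will therefore look for a renal comparison by arm.

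Day 364 is a poor single time point for it, for two reasons. The tacrolimus trough target is 5-10 ng/mL at Visits 2-6 and below 5 ng/mL at Visits 7-9 (SAP 5.2.1), and Protocol 8.1.1 describes the listed tacrolimus reactions as reversible or lessened by dose reduction. (The MMF target also falls, from an AUC of 30-50 to at most 40 µg.h/mL.) And a child withdrawn earlier, including one withdrawn under the renal or liver rule, has no Day 364 result.

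A crossing that occurs during the higher-exposure months, resolves, and is not reported as an adverse event would then be missing from every safety-set count by arm.

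**Working it through.** The plan states no figure on this point, so the check is mainly a reading of the table shells, with short arithmetic.

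**1. Visit coverage.** Post-baseline visits with these tests: Days 7, 28, 56, 112, 168, 224, 280 and 364, which is 8. The safety-set shift tables use 1, leaving out 7/8 = 87.5%. The Table 23 shell, reused for the other by-visit tables, prints Visits 2 and 4-9, which is 7 of 8; Visit 3 (Day 28) is absent.

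**2. What each output gives.**

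| Output | Set | Visits | Count by arm at the plan's levels? |
|---|---|---|---|
| Shift Tables 82-92, 96-98, 104 | Safety | Day 364 only | No; judgement categories |
| Tables 23-27, 41-49 | FAS/PPS | 7 of 8 | No; mean, quartiles, min, max |
| Listings 123, 125 | Safety | By visit | No; per child, normal to abnormal only |
| AE Tables 62-66 | Safety | Any time | Only what is reported as an AE |
| Table 3 | All enrolled | Any time | No; discontinuation reasons, none naming a laboratory level |

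The FAS also leaves out eliminated cases (SAP 7.1), so the by-visit tables can omit safety-set children.

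**3. The renal levels.** eGFR = K x height / SCr (Protocol Appendix 1). At fixed K and height, new SCr / baseline SCr = baseline eGFR / new eGFR.
- Entry requires eGFR of at least 90. Falling below 60 therefore needs a ratio above 90/60 = 1.5, a rise of more than 50%. The 30% condition never binds, and the laboratory part of the tacrolimus dose rule reduces to eGFR below 60.
- The withdrawal rule is different. From a baseline of 60 x 2 = 120 or more, creatinine can double while eGFR stays at 60 or above, so both parts of that rule are needed.

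**4. What the listings catch and miss.** A child who enters at 90 or above and falls below 60 goes from normal to abnormal and should appear in Table 125, with arm and visit but without a tally. For ALT, SAP 4.5.2 (6) excludes only values at twice the upper limit or more with a continuing 2-week rise. A child can therefore enter with a raised ALT, later pass twice the limit, and be absent from Table 123, because the baseline was not normal.

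**5. Children without a Day 364 value.** With 135 per arm and the plan's 15% loss, 135 x 0.85 = 114.75 per arm have a value. About 20 per arm (135 x 0.15 = 20.25) do not.

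**6. Precision of a worst-value table.** The documents give no laboratory event rates, so these counts are assumptions, with n = 135 per arm and Newcombe 95% intervals:
- 3 v 0: 2.2 points (-0.9 to 6.3)
- 6 v 0: 4.4 points (0.8 to 9.4)
- 6 v 2: 3.0 points (-1.5 to 8.0)

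Two-sided Fisher power against a true rate of 0% is 5.5% at a 2% rate, 22% at 3% and 67% at 5%.

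**The case against.** The case against is that the important crossings are already visible. A child who meets the withdrawal rule must leave. The laboratory reason then becomes a reportable adverse event and should reach the drop-out row of Table 62 and the reasons in Table 3. By-visit minima and maxima show whether any analysed child crossed a level at that visit. Table 125 lists any protocol-eligible child who falls below 60. All of this stands, and it narrows the gap to three things: the count itself, transient crossings nobody reported, and children whose baseline was already abnormal.

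Three stronger readings are tempting, and the documents do not support them.

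- **That only drug-related or serious events are collected.** Protocol 8.3 names "Adverse events related to the test drugs (according to the judgment of the investigators" among the information to collect, but it says the information includes these aspects. It also requires all adverse events of concern under 8.1.1 and 8.1.2, which cover kidney injury and abnormal liver function. Table 63 has rows for events unlikely to be related and not related.
- **That a 30% creatinine rise alone, or a doubling alone, is a plan level.** Both renal rules also require eGFR below 60.
- **That relapse will empty the Day 364 column unequally.** A note to Table 1 says "Subjects who withdrew due to the endpoint event were considered to have completed the trial", and SAP 4.2.2 states "It is estimated that 1-year relapse-free survival is 0.56 in MMF Group, and 0.70 in FK506 Group". If every relapser left, with loss independent of relapse, 114.75 x 0.56 = 64 MMF and 114.75 x 0.70 = 80 tacrolimus children would remain. That is an extreme. Relapse is not a mandatory withdrawal reason, SAP 5.2.2 continues the study drug after relapse, and relapse frequency and whole-study steroid dose need follow-up beyond it. The share who leave is unknown, and the shift shell shows missing values by arm.

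**Conclusion.** The point holds in a limited form. Safety-set categories for renal and liver laboratory results use one of eight post-baseline visits, at a time of low tacrolimus exposure. No output counts by arm the children whose worst value crossed the plan's levels. Transient crossings not reported as adverse events are uncounted, as is an ALT raised at entry that later passes twice the upper limit. The documents do not allow the number of such children, or the direction of any bias, to be estimated.

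This assumes that the flow chart governs. Protocol 8.3 says laboratory safety assessment is not routine after baseline, but the flow chart and the by-visit table shells imply that it is. The eGFR arithmetic assumes fixed height and entry at 90 or above.

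The primary analysis is not affected. This is a cheap improvement of minor weight.

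**What to change.** Add one descriptive safety-set table by arm, using each child's worst post-baseline value at any visit up to withdrawal, Visit 3 included. Rows:
- eGFR below 60 (for children entering at 90 or above, equivalent to the laboratory part of the tacrolimus dose rule);
- creatinine more than twice baseline on two consecutive measurements at least 4 weeks apart, with eGFR below 60;
- ALT or total bilirubin above twice the upper limit.

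For each row give number, percentage and risk difference with 95% CI. Put the scheduled-visit count beside the any-visit count, because unscheduled testing may differ by arm in an open-label trial. Show the number of children with at least one post-baseline value, and person-years, in case follow-up differs. Creatinine up by at least 30% alone, or more than doubled alone, may be added only if labelled as supplementary thresholds that are not action rules in the plan. Blood-count rows are optional.

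Cite the table beside the adverse-event tables in SAP 8.1.6 and keep the Day 364 shift tables as supportive. The cost is one derived table and one sentence, from values already scheduled. The downside is low precision for rare events, so the table should stay descriptive.
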